10.5 Glucose, insulin & HbA1c

A shift table using CTCAE grades will be produced for these parameters to compare baseline and the worst on-treatment value with each laboratory parameter on a new page. Percentages will be calculated using the number of available patients at baseline with corresponding grade and at least one non-missing post baseline value as the denominator.

For laboratory tests where CTCAE grades are not defined, a shift table using the low/normal/high/(low and high) classification will be produced to compare baseline to the worst on-treatment value with each laboratory parameter on a new page. Percentages will be calculated using the number of available patients at baseline with corresponding level and at least one non-missing post baseline value as the denominator.

Tables created as part of the extension phase analyses will be repeated excluding patients missing glucose, insulin and HbA1c assessment during Extension study phase.

A listing will be provided split by treatment arm summarizing this information and will include visit, sample date, laboratory number, laboratory name, glucose, insulin, HbA1c and a flag to indicate whether it was taken whilst fasting.

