6.1.4.5.1 Monitoring of glucose levels

For patients in the pasireotide LAR monotherapy arm and in the pasireotide LAR and everolimus combination arm

All patients in the combination arm and in pasireotide LAR monotherapy arm must self-monitor glucose levels.

Patients with normal glucose metabolism at baseline should self-monitor their fasting blood glucose level once daily by fingerstick for the first 2 months, then twice a week for the next 2 months and once a week thereafter throughout the study.

Patients with a prior history or newly observed fasting hyperglycemia, impaired glucose tolerance or diabetes mellitus, or at risk of developing these conditions should self monitor their blood glucose by fingerstick twice daily (once fasting and once 2-hours post-prandial). The site should call the patient after approximately 10 days after day 1 and day 29 visits (i.e. for the first 2 cycles) and should ask for the blood glucose results.

All patients should contact the site (or medical care, if the site is unavailable) if the fasting blood glucose level is >130 mg/dL (7.2 mmol/L) on any two separate occasions and come for an additional visit as soon as possible to confirm the values and to ensure early intervention.

Any patient should contact the site (or medical care, if the site is unavailable) immediately if the fasting blood glucose value is ≥ 200 mg/dL (11.1 mmol/L) at any time. At this visit, fasting plasma glucose levels will be measured at local lab. Patients with confirmed fasting hyperglycemia should start self-monitoring of their blood glucose by fingerstick twice daily (once fasting and once 2-hours post-prandial), if not already done. They may be also be referred to a specialist for appropriate management of hyperglycemia. In order to ensure early intervention, if needed, glucose levels will be tested at the local lab at all visits.

All patients will keep a diary for appropriate detection and management of hyperglycemia throughout the trial and present the collected data to their physician/diabetes specialist for evaluation. The sponsor will provide the patient diaries but this data will not be collected by the sponsor.

For patients in the everolimus monotherapy arm

All patients in the everolimus monotherapy arm showing \geq grade 3 hyperglycemia (>250 mg/dL; >13.9 mmol/L) at any point visit throughout the study, should start monitoring their blood glucose by fingerstick twice daily (once fasting and once 2 hours post-prandial).

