7.2.2.5.4 Glucose, Insulin and HbA1c

Glucose, insulin, and glycated hemoglobin (HbA1c) will be assessed in fasting conditions at the visits outlined in [Table 7-1](#) and in [Table 7-2](#).

Blood glucose will not be assessed at visit 6 in patients treated with everolimus monotherapy, unless medically indicated.

Please refer to [Section 6.1.4.5](#) for additional detailed guidance on the combination and pasireotide LAR monotherapy arms.

For patients in the combination and pasireotide LAR monotherapy arms with normal glucose metabolism at baseline, fasting blood glucose will be self-measured once daily for the first 2 month, then twice a week for the next 2 months and once a week thereafter throughout the study.

All patients with abnormal glucose metabolism or at risk to develop this condition at screening or later at any time will self-measure blood glucose by fingerstick twice daily (one fasting and one 2-hour post-prandial). All patients will enter the results in the patient diary. Patient diaries will not be collected by the sponsor.

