9.4 Database management and quality control

Novartis personnel (or designated CRO) will review the data entered by investigational staff for completeness and accuracy. Electronic data queries stating the nature of the problem and requesting clarification will be created for discrepancies and missing values and sent to the investigational site via the EDC system. Designated investigator site staff is required to respond promptly to queries and to make any necessary changes to the data.

Concomitant treatments entered into the database will be coded using the WHO Drug Reference List, which employs the Anatomical Therapeutic Chemical classification system. Medical history/current medical conditions and adverse events will be coded using the Medical dictionary for regulatory activities (MedDRA) terminology.

10 Statistical methods and data analysis

This is a multicenter, phase II trial evaluating the treatment of pasireotide LAR and everolimus in patients with well differentiated neuroendocrine carcinoma of the lung and thymus randomized to one of the following arms:

- Arm 1: pasireotide LAR alone;
- Arm 2: everolimus alone;
- Arm 3: pasireotide LAR and everolimus.

The study is designed to assess the activity, safety, and tolerability of the therapy with pasireotide LAR and/or everolimus in each arm separately following a Fleming single-stage design. Each arm is independently evaluated using the decision rules given in the sample size calculation (see [Section 10.8](#)). If 2 or 3 arms are accepted the selection of the best arm will be based on a risk/benefit evaluation including the incidence of grade 3-4 adverse events, the incidence of serious adverse events, the frequency of treatment modifications as key safety parameters to be taken into account in the final decision.

The data will be analyzed by Novartis and/or by the designated CRO. Any data analysis carried out independently by the investigator(s) should be submitted to Novartis before publication or presentation. It is planned that the data from participating centers in this protocol will be combined within each of the arms, so that an adequate number of patients will be available for analysis.

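### Hyperglycemia is looked for more closely in the two pasireotide arms than on everolimus alone, and no planned glucose table limits the comparison to scheduled visits common to all arms

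*SAP*

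**What the plan says.** **Monitoring in the pasireotide-containing arms (Protocol 6.1.4.5.1).** "All patients in the combination arm and in pasireotide LAR monotherapy arm must self-monitor glucose levels". The frequency depends on baseline status: "Patients with normal glucose metabolism at baseline should self-monitor their fasting blood glucose level once daily by fingerstick for the first 2 months". Testing drops to two readings weekly over another two months, and to one weekly after that. Patients with abnormal glucose metabolism, or at risk of it, test twice daily. In the paragraph on those patients the protocol adds: "The site should call the patient after approximately 10 days after day 1 and day 29 visits". Any patient in these arms with two fasting readings above 130 mg/dL must contact the site and "come for an additional visit as soon as possible to confirm the values and to ensure early intervention". One fasting reading of 200 mg/dL or more calls for immediate contact. Plasma glucose is then measured at the local laboratory.

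**Monitoring on everolimus monotherapy.** The arm-specific rule starts fingersticks after hyperglycemia of grade 3 or worse (above 250 mg/dL) at a visit. A separate all-patient rule starts twice-daily fingersticks in any arm after fasting glucose above 130 mg/dL or post-prandial glucose of at least 180 mg/dL on two occasions, and/or HbA1c above 7%. Protocol 7.2.2.5.4 states: "Blood glucose will not be assessed at visit 6 in patients treated with everolimus monotherapy, unless medically indicated". The same section has abnormal or at-risk patients self-measure, without naming an arm. The diaries are not collected by the sponsor.

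**Analysis.** SAP 10.5: "A shift table using CTCAE grades will be produced for these parameters to compare baseline and the worst on-treatment value". SAP 10.1 tabulates treatment-emergent events, grade 3-4 events and special-interest groupings by arm, and SAP 5.4.1 tabulates dose reductions and interruptions. SAP 3.9.1 says that data from unscheduled visits are listed, but not whether they can supply the worst value.

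**Use.** Under Protocol section 10, if two or three arms are accepted, the best is chosen by a "risk/benefit evaluation including the incidence of grade 3-4 adverse events", serious events and treatment modifications. SAP 6.3.2 adds guidance from a Bayesian ranking on progression-free status at Month 9.

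**The concern.** Incidence depends on how hard one looks. Two arms have a standing search for raised glucose between visits, and the third does not until something has already been found. Fingerstick readings are not study data themselves, but they produce site contacts and local laboratory values. Protocol 7.2.2.5 sends clinically relevant unscheduled abnormal values to the adverse event page. Protocol 8.1.1 makes a value an adverse event if it is clinically significant or needs therapy or a change in study drug. Protocol 6.1.4.5.2 interrupts study drug at grade 3 or worse. Unequal testing can therefore reach the adverse event, grade 3-4 and treatment-modification counts.

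These are the safety parameters named for choosing between accepted arms, and that step was reached. The Amendment 5 rationale reports 13/41, 14/42 and 13/41 patients progression-free (31.7%, 33.3%, 31.7%). With efficacy this close, safety may carry the choice. Hyperglycemia is the event that Protocol 1.2.1.3 singles out as more frequent with pasireotide. Neither document comments on the unequal ascertainment.

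**Working it through.** The plan states no figure for ascertainment. The only plan figure on this route is the Fleming rule that opens the selection step, and it reproduces: P(X ≥ 13 | n = 40, p = 0.20) = 4.3% and P(X ≤ 12 | n = 40, p = 0.45) = 3.9%, against the stated 4.3% and 4%.

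1. **Planned fingersticks, core year of 364 days, normal glucose at baseline, pasireotide arms.** With a 28-day month: 56 daily + 16 at two per week + (364 − 112)/7 = 36 weekly = 108. With a 30.4-day month: about 61 + 17 + 35 = 113. Twice-daily testing all year gives 2 × 364 = 728. On everolimus monotherapy the number is 0 until a trigger is met (under 7.2.2.5.4, at-risk patients might be an exception).

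2. **Scheduled laboratory glucose after Day 1 (Table 7-1).** Everolimus: days 15, 21, 29, 57, then every 28 days from 85 to 337, then 365 = 15 values. Pasireotide arms: the same plus Day 49 = 16. The scheduled laboratory series is nearly balanced; the imbalance lies in what happens between visits.

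3. **Share of episodes that a scheduled everolimus visit would catch.** Assume one episode of L days with onset uniform in time. It is caught if a visit falls inside it, that is, if onset lies within L days before a visit.
   - First eight weeks (onset days 1 to 57, width 56; visits 15, 21, 29, 57). L = 7: onset intervals 8–21, 22–29 and 50–57 give 13 + 7 + 7 = 27, and 27/56 = 48%. L = 14: intervals 1–29 and 43–57 give 28 + 14 = 42, and 42/56 = 75%.
   - Later in the core phase (visits 28 days apart): min(1, L/28) = 25% for 7 days, 50% for 14, 75% for 21 and 100% for 28 or more.
   - Extension (visits about 91 days apart): 7/91 = 8% and 14/91 = 15%. Weekly fingersticks continue in the pasireotide arms, and SAP section 10 reruns safety on core and extension data combined.
   - With full adherence, weekly or more frequent fingersticks put at least one reading inside any episode of 7 days or longer.

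4. **Effect on an incidence comparison (illustration).** Suppose true incidence π is equal in all arms, each affected patient has one short episode, detection is complete in the pasireotide arms and is d on everolimus. The apparent excess is π(1 − d). For π from 20% to 40% and d from 75% to 50% (the 14-day values), it runs from 0.20 × 0.25 = 5 points to 0.40 × 0.50 = 20 points, or 2 to 8 patients of 40. For episodes of 28 days or more it is zero in the core phase.

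5. **What step 4 leaves out.** It concerns detection only. Protocol 6.1.4.5 suggests that suboptimal glucose monitoring may have contributed to the high grade 3 rate in earlier studies. Contact is triggered at 130 mg/dL, well below the grade 3 limit of 250 mg/dL. Closer monitoring may therefore lower grade 3-4 counts in the monitored arms, so the net sign at grade 3-4 cannot be derived from the documents.

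**The case against.** The case against is substantial.

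- The SAP 10.5 shift table rests on laboratory values, scheduled 16 against 15 times, and diaries are not collected. It is the output least exposed. This stands, except that the SAP leaves open whether values from triggered visits count as worst on-treatment.
- HbA1c is drawn on nearly the same schedule in all arms and has its own shift table in SAP 10.5, so a nearly balanced comparison already exists. This stands, although HbA1c does not give a graded count of glucose excursions.
- A reading inside an episode is not an adverse event. At 131 to 199 mg/dL two readings are needed to trigger contact, so a 7-day episode under weekly testing may trigger nothing. Complete detection is therefore an upper bound.
- No document gives episode durations, and sustained hyperglycemia would be found in every arm.
- Arm selection is a qualitative judgement that does not name hyperglycemia, and no between-arm safety test is planned. The link is indirect, but it runs through criteria that the protocol does name.

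A reader might infer that everolimus patients are followed at scheduled visits only. The all-patient trigger contradicts that, and 7.2.2.5.4 may widen self-testing further. A reader might also infer that grade 3-4 hyperglycemia is inflated in the pasireotide arms; the documents give a reason for the opposite as well. Nor do they support replacing adverse events by laboratory values in the selection step: the protocol's criterion is grade 3-4 adverse events, and glucose at scheduled visits is itself affected by earlier treatment in the monitored arms.

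**Conclusion.** The point holds in a limited form. Surveillance differs by design, and hyperglycemia adverse events, grade 3-4 events and dose modifications are open to differential ascertainment in contrasts with everolimus monotherapy. Pasireotide alone against the combination is unaffected, because both follow the same rules. The size depends on an assumed episode length: an apparent excess of 5 to 20 points for 14-day episodes under the assumptions in the working, and none in the core phase for episodes of 28 days or more. Those figures describe detection of short episodes with full adherence. At grade 3-4 the direction is unknown. This warrants an inexpensive supportive analysis; it does not show that the planned tables are wrong.

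**What to change.** Keep the planned adverse event and worst-value tables and the protocol's grade 3-4 adverse event criterion.

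- In SAP 10.5, add one supportive between-arm table of worst CTCAE grade of fasting laboratory glucose, restricted to scheduled visits common to all arms. Leave out Day 49 and all unscheduled or fingerstick-triggered values. Read it with the existing HbA1c shift table in the arm-selection evaluation.
- State whether unscheduled values count as worst on-treatment in the existing glucose shift table.
- In SAP 10.1 and 5.4.1, footnote the hyperglycemia adverse event and dose-modification tables as not equally ascertained against everolimus monotherapy.
- Reconcile Protocol 6.1.4.5.1 and 7.2.2.5.4 on which everolimus patients self-monitor, so that the footnote can describe the difference correctly.

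The cost is a few lines of SAP text and one table from data already collected. The added table will miss short episodes between visits and will not remove any effect of earlier glucose treatment in the monitored arms. Nothing in monitoring or clinical management changes.

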10.6 Serum lipid profile

A shift table using CTCAE grades will be produced for these parameters to compare baseline and the worst on-treatment value with each laboratory parameter on a new page. Percentages will be calculated using the number of available patients at baseline with corresponding grade and at least one non-missing post baseline value as the denominator.

For tests where CTCAE grades are not defined, a shift table using the low/normal/high/(low and high) classification will be produced to compare baseline to the worst on-treatment value with each laboratory parameter on a new page. Percentages will be calculated using the number of available patients at baseline with corresponding level and at least one non-missing post baseline value as the denominator.

A listing will be provided split by treatment displaying the visit, sample date, laboratory number, laboratory name, cholesterol, triglycerides, LDL and HDL.

10.7 Thyroid function

Thyroid function tests of thyroid stimulating hormone (TSH), free T3 (tri-iodothyronine) and T4 (levothyroxine) along with B12 vitamin will be collected at baseline, week 12, week 24 and at the end of the core study. Plasma ACTH will be taken at baseline and only those patients with hypersecretion will be tested again.

A shift table using CTCAE grades will be produced for these parameters to compare baseline and the worst on-treatment value with each laboratory parameter on a new page. Percentages will be calculated using the number of available patients at baseline with corresponding grade and at least one non-missing post baseline value as the denominator.

For laboratory tests where CTCAE grades are not defined, a shift table using the low/normal/high/(low and high) classification will be produced to compare baseline to the worst on-treatment value with each laboratory parameter on a new page. Percentages will be calculated using the number of available patients at baseline with corresponding level and at least one non-missing post baseline value as the denominator.

This information will also be presented in a listing along with the visit, sample date, laboratory number and laboratory name split by treatment.

10.8 Electrocardiograms (ECGs)

Overall ECG interpretation and details of abnormalities are collected at Screening and selected visits. The ECG QTcF result at each visit will be categorized. A shift table displaying the baseline categorized ECG QTcF result compared with the worst post-baseline categorized result will be produced. Percentages will be calculated using the number of patients with that categorized result at baseline as the denominator.

The number of patients recording notable ECG QTcF increases from baseline at least once will also be presented. Percentages will be calculated using the number of patients with both baseline and post baseline evaluations.

A listing of ECG evaluations will be presented for all patients with at least one treatment emergent abnormality i.e. where no clinically significant abnormality was present at baseline and a clinically significant abnormality was present on-treatment. This listing will include the date of ECG, clinically significant abnormality (yes, no) and abnormality descriptions.

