10.5.3.1.4 Other safety data

ECG

- Data from ECG will be listed and notable values will be flagged.
- Shift table from baseline to worst on-treatment result and summary statistics of changes from baseline will be provided for QTcF.

Number and percentage of patients with clinically notable QTcF interval values will be summarized.

Vital signs

Vital signs variables include measurements of oral body temperature, systolic and diastolic blood pressures, pulse and body weight.

Data on vital signs will be descriptively analysed and listed. Notable values will be flagged; definitions of notably abnormal results will be specified in the statistical analysis plan.

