10.2 Laboratory values

All laboratory values will be converted into SI units; for laboratory tests covered by the CTCAE version 4.0 (see National Cancer Institute (NCI) 2009), the study's biostatistical and reporting team will grade laboratory data accordingly. For laboratory tests covered by CTCAE, a Grade 0 will be assigned for all non-missing values not graded as 1 or higher. Grade 5 will not be used. For laboratory tests where grades are not defined by CTCAE, results will be graded by the low/normal/high classifications based on laboratory normal ranges.

All summaries will be produced separately for each lab category (hematology, biochemistry and urinalysis). Hematology includes hemoglobin, hematocrit, platelets and total white blood cell count (WBC, absolute & differential including neutrophils, lymphocytes, monocytes, eosinophils and basophils). Biochemistry includes sodium, potassium, chloride, bicarbonate, creatinine, total protein, uric acid, blood urea nitrogen (BUN), calcium, magnesium and phosphate. Urinalysis includes pH, protein, glucose, blood, ketones and leukocytes. They will be tested using a dipstick. In some cases urea results will be collected rather than BUN. In these cases urea will be converted to BUN using the following conversions:

$$\text{BUN (mg/dL)} = \text{Urea (mg/dL)} / 2.14$$

$$\text{BUN (mmol/L)} = \text{Urea (mmol/L)} / 2$$

Shift tables using CTCAE grades will be produced for hematology and biochemistry separately to compare baseline and the worst on-treatment value with each laboratory parameter on a new page. Percentages will be calculated using the number of available patients at baseline with corresponding grade and at least one non-missing post baseline value as the denominator.

For laboratory tests where CTCAE grades are not defined, shift tables using the low/normal/high/(low and high) classification will be produced to compare baseline to the worst on-treatment value with each laboratory parameter on a new page. Percentages will be calculated using the number of available patients at baseline with corresponding level and at least one non-missing post baseline value as the denominator.

The following rules will be applied to derive the WBC differential counts when only percentages are available (this is mainly important for neutrophils and lymphocytes, as the CTC grading is based on the absolute counts).

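### SAP 10.8 leaves out the protocol's summary of QTcF change from baseline and lists ECGs only for a subset of patients

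*SAP*

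**What the plan says.** Protocol 10.5.3.1.4 (Other safety data) specifies the ECG outputs in three sentences:

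- Listing: "Data from ECG will be listed and notable values will be flagged". No subset of patients is named.
- QTcF over time: "Shift table from baseline to worst on-treatment result and summary statistics of changes from baseline will be provided for QTcF".
- Notable values: "Number and percentage of patients with clinically notable QTcF interval values will be summarized".

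SAP 10.8 (Electrocardiograms) plans three outputs:

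- A shift table: "A shift table displaying the baseline categorized ECG QTcF result compared with the worst post-baseline categorized result will be produced". Its denominator rule is: "Percentages will be calculated using the number of patients with that categorized result at baseline as the denominator".
- A count: "The number of patients recording notable ECG QTcF increases from baseline at least once will also be presented". Here the denominator is patients who have both a baseline and a post-baseline evaluation.
- A listing of ECG evaluations, only for patients "where no clinically significant abnormality was present at baseline and a clinically significant abnormality was present on-treatment". The fields it names are the ECG date, whether a clinically significant abnormality was present, and its description.

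For comparison, the shift tables in SAP 10.2 (Laboratory values) require the patient to have "at least one non-missing post baseline value as the denominator".

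**The concern.** QT prolongation is a documented effect of one of the two study drugs. Protocol 6.1.4.9 says that subcutaneous pasireotide prolonged the QT interval in healthy subjects in two Phase I studies, and two of the three arms here receive pasireotide LAR. The protocol therefore asks for a continuous summary of QTcF change as well as categories.

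Followed as written, SAP 10.8 drops that summary. A count of patients above a threshold does not show the average or the spread of the change. SAP 10.8 also does not state its QTcF category bounds or what counts as a notable increase. The omitted table is the one QTcF output that needs no cut-off.

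The listing rule removes a patient who enters with a clinically significant abnormality and then worsens. Such patients can be enrolled: Protocol 7.2.2.7.1 has significant findings discussed with the medical monitor before enrolment. SAP 10.1 counts adverse events that worsened as treatment-emergent, so the ECG listing is stricter than the SAP's own convention for events.

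**Working it through.** **Comparison of required and planned outputs**

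1. *QTcF shift table.* Required by the protocol and planned in SAP 10.8. It is present.
2. *Summary statistics of QTcF change from baseline.* Required by the protocol. SAP 10.8 has only the count of notable increases, so this output is absent.
3. *ECG listing with notable values flagged.* Required without restriction. SAP 10.8 imposes two conditions, no clinically significant abnormality at baseline and one on treatment. It names neither the QTcF value nor a flag among the fields. The listing is narrower than required.
4. *Consistency within the SAP.* SAP 10.1, in the adverse event section, says that all safety data will be listed. SAP 10.8 does not do that for ECGs, so the two statements need reconciling.
5. *Declaration.* SAP Section 2 says that one discrepancy with protocol version 05 exists. The readable text concerns confidence intervals. Part of the section is redacted.

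**Shift-table denominator**

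The plan states no figure to reproduce. The size follows from a ratio. Let n be the patients in a baseline QTcF category, m those among them with no post-baseline ECG, and x those who shift.

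- Percentage under SAP 10.8: x/n.
- Percentage among patients who could shift: x/(n − m).
- Ratio of the first to the second: (n − m)/n.

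Can m exceed zero? Under SAP 3.7 the safety set needs one post-baseline safety assessment of any kind, and a statement of no adverse events suffices. A patient without a post-baseline ECG can therefore be counted. The documents do not give m.

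Illustration, with assumed values: n = 41, the number of patients in the pasireotide LAR arm and in the combination arm (Protocol, Amendment 5 rationale), all placed in one baseline category, and x = 4. Under SAP 10.8 the result is 4/41 = 9.8%. Among evaluable patients:

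- m = 0: 4/41 = 9.8%, ratio 1.00
- m = 2: 4/39 = 10.3%, ratio 39/41 = 0.95
- m = 4: 4/37 = 10.8%, ratio 37/41 = 0.90
- m = 8: 4/33 = 12.1%, ratio 33/41 = 0.80

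The largest gap in this range is 12.1 − 9.8 = 2.3 percentage points. The real table splits each arm by baseline category, so the ratio depends on n and m within each category. The count of notable increases is not affected, because its denominator already requires a post-baseline evaluation.

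**The case against.** The strongest defence is that other text fills the gap. SAP Section 1 says that data will be analysed according to Section 10 of the protocol. SAP 3.2 promises that changes from baseline in ECG tracings will be reported. SAP Section 4 allows continuous data to be collapsed into categories. These are general statements. None supplies the specific table, and a general presentation rule does not cancel a specific protocol output.

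Several stronger readings are tempting, and here the defence is right:

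- *A reader might infer that worsening in patients with a baseline abnormality goes unreported.* It should not. Protocol 7.2.2.7.1 sends new or worsened significant ECG findings to the adverse event page, and SAP 10.1 tabulates and lists those events. The count of notable QTcF increases also applies whatever the baseline status. Second- or third-degree AV block in Protocol 7.1.4.1 is a Holter finding, so it is not an example of what the routine ECG listing misses. The exclusion criteria (baseline QTcF above 470 msec, significant arrhythmia, symptomatic bradycardia, high-grade block) should also keep the number of such patients low.
- *A reader might infer that shift percentages are biased low in arms with more dropout.* The documents do not establish this. Protocol 7.1.4 requires the full end-of-core assessments at early withdrawal, and Table 7-1, as far as its layout can be read, includes an ECG at that visit. SAP Section 4 adds a row for missing data, which would make such patients visible, although it would not change the denominator.
- *A reader might infer that the baseline-only denominator is peculiar to ECGs.* SAP 10.13 and 10.16 use it too. It differs from the laboratory and vital-sign tables (SAP 10.2, 10.15) and from the next paragraph of SAP 10.8.
- *A reader might infer that the mean QTcF change is the most precise measure of this harm.* No precision calculation supports that, and the protocol asks only for descriptive statistics.

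**Conclusion.** The departure from the protocol stands. SAP 10.8 omits the summary statistics of QTcF change and restricts an ECG listing that the protocol leaves unrestricted. The loss is the continuous QTcF summary and the ECG record behind any worsened finding. The clinical event itself should still appear in the adverse event outputs. Whether the departure is declared cannot be settled, because SAP Section 2 is partly redacted; its readable part does not mention it.

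The denominator is a minor inconsistency. Its effect is (n − m)/n within each baseline category and is zero if every patient has a post-baseline ECG. The figures above rest on assumed values of m and x and on a single baseline category, and they are not estimates for this trial.

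This is a secondary safety output with no bearing on the primary endpoint. It should be corrected because the risk is known and because the choice between arms rests on a risk/benefit evaluation (Protocol Section 10, SAP 6.3.2), although QTcF is not among the key safety parameters named there.

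**What to change.** In SAP 10.8:

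1. Add descriptive statistics of QTcF change from baseline by arm, by visit and to the worst on-treatment value.
2. List all ECG data, including QTcF values, with notable values and new or worsened abnormalities flagged, whatever the baseline status. This also removes the conflict with SAP 10.1.
3. Use patients in the given baseline category with at least one post-baseline QTcF as the shift-table denominator.

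If the sponsor prefers the reduced outputs, SAP Section 2 should declare and justify them.

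The cost is SAP wording, one more standard table and a longer listing. SAP Section 10 already plans to rerun all safety analyses and listings on cumulative data after the extension phase, so the change fits there. No new data are needed, and no clinical rule changes.
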